### 4.3.2 TRANSTHORACIC ECHO REQUIREMENTS

A local hospital transthoracic echocardiography (TTE) performed within the previous 6 months of the ablation procedure will be required. The following measurements will be collected:

- LVEF (biplane Simpson's method) (%)
- LVEDD and LVESD (paraesternal long axis 2D) (mm)
- LVEDV and LVESV (biplane Simpson's method) (mL or mL/m^2)

Of note is that three consecutive averaged beats will have to be computed to minimize distortion generated in case of frequent PVCs during exploration. The echocardiographic evaluation will not include ectopic or post-ectopic cycles.

### 4.3.3 CARDIAC MRI REQUIREMENTS

If available, a local hospital cardiac magnetic resonance imaging (MRI) would be advisable, also within the previous 6 months. If not performed before, it can be scheduled in the enrollment or baseline visits as long as it is suitable according to hospital characteristics. Image acquisition protocols must include late gadolinium enhancement (LGE) sequences. The following measurements will be collected:

- LVEF (%)
- LVEDD and LVESD (mm)
- LVEDV and LVESV (mL or mL/m^2)
- Presence, location (subendocardial, intramyocardial, subepicardial, transmural) and distribution (linear, patchy, etc.) of LGE, if any.

#### 4.4 BASELINE VISIT

The baseline visit must be performed after the patient has signed the informed consent form and prior to the PVC ablation procedure. The patients will be evaluated clinically and the following data will be collected and procedures performed:

- Patient demographic data
- Clinical evaluation with a physical examination
- Medical and cardiovascular history
- Pre-procedure MRI (optional, see before)
- Current cardiac medication (antiarrhythmic drugs and beta-blockers should have been withdrawn at least for 5 half-lives before the procedure)
- NYHA class assessment
- 12-lead ECG
- Adverse Events Notification (if applicable)
- Protocol Deviation (if applicable)
- Termination (if applicable)

#### 4.5 RANDOMIZATION AND ABLATION

##### 4.5.1 RANDOMIZATION

Patients will be randomly assigned to each of the annotation systems (WF vs. M-method) on a 1:1 basis before the procedure as described in chapter 2.2.

##### 4.5.2 ELECTROPHYSIOLOGIC STUDY

Electroanatomical mapping (EAM) will be performed using the CARTO® navigation system (Biosense Webster, Diamond Bar, CA) with a 3.5-mm irrigated tip catheter (NaviStar® ThermoCool® or ThermoCool® SmartTouch®, Biosense Webster). During the procedure, 12-surface ECG and intracardiac recordings will be displayed by an electrophysiology data acquisition system (Bard LabSystem, CR Bard Inc, Lowell, MA; or EP-Tracer, CardioTek, Maastricht, The Netherlands).

##### 4.5.3 ACTIVATION MAPPING. ANNOTATION SYSTEMS.

The cardiac structures that will be targeted during activation mapping will be decided according to PVC morphology in surface ECG and operator's criteria. A detailed activation map of the cardiac chamber/s suspected to contain the SOO of the will be performed in all patients:

- In those cases with a suspected outflow tract origin, mapping will be guided by a proposed algorithm (see Appendix C) that includes a previously described clinical score (1 point for

each of the following: hypertension, male gender, age > 50 years). With this algorithm, an accurate prediction of left vs. right ventricular outflow tract origin is expected.

- After applying the previous algorithm and having completed RVOT mapping, if a focus outside the RVOT is suspected, subsequent mapping of the coronary sinus may be advisable to add useful information of the left side and possible epicardial origin of the PVCs.
- The minimum density of points required to obtain an acceptable map will be defined as a fill threshold of < 6 mm in the 20-ms isochronal area containing the earliest activation site (area of interest), and < 10 mm for the chamber of interest.

An ECG surface lead with a well-defined R-wave peak (R peak = 0 ms) will be used as the reference to perform the activation EAM. For both annotation systems, the end of the window of interest will be set at the end of the PVC-QRS to avoid the annotation of atrial far-field signals (in cases with retrograde conduction of the PVC). During activation mapping, points will be acquired only after a 2-second period of catheter stability. Activation mapping of additional anatomical structures will be allowed under operator criteria, in cases where the suspected SOO could not be located at the initially mapped chamber. Regardless of the number of structures mapped during the procedure, the annotation system will be the one assigned at the beginning of the procedure. The earliest activation site (EAS) will be considered to be located at the point with the highest precocity relative to the earliest onset of PVC on the 12-lead surface ECG, when activation mapping has concluded.

#### 4.5.3.1 MANUAL ANNOTATION (M-METHOD):

A detailed electrocardiogram (ECG)-gated activation map of the chamber of interest will be acquired using the CARTO system. An experienced electrophysiologist will perform the annotation of LAT in each acquired point. The LAT will be measured from the onset of B-EGM (earliest positive or negative deflection) of the distal bipole of the mapping catheter to the defined reference. The use of the U-EGM as a guidance to identify the real onset of B-EGM will be decided under electrophysiologist criteria.

#### 4.5.3.2 AUTOMATIC ANNOTATION (WF-METHOD):

The annotation of LAT in each acquired point will be automatically performed using the LAT annotation tool integrated into CARTO system, Wavefront (WF). Automatic annotation of LAT performed by the CARTO system uses the maximum negative slope of the distal U-EGM to set the timing of the mapping annotation, displayed on the corresponding B-EGM. Additionally, the automatic annotation of LAT will be aided by the ECG recognition pattern

algorithm (included in the last version of CARTO), which is intended to avoid wrong annotation of ventricular complexes other than the clinical PVC.

#### 4.5.4 ABLATION

Ablation will be directed to the earliest activation site identified with the assigned annotation system. A target point will be defined as any suspected PVC-SOO, where RF is delivered, according to mapping data. The temperature limit will be set at 45°C. Power limit will be set according to the anatomical structure containing the SOO: 40 W for the RVOT and the subvalvular LVOT, 30-40 W in the aortic root, and 20 W in the coronary sinus. If RF application is successful, it will be maintained for 60 seconds in cases of RVOT PVCs, and for 30-45 seconds when PVCs arise from the LVOT or distal CS. The point at which radiofrequency application is successful will be tagged as the effective RFp (e-RFp). If PVCs persist after a 30-second application, RF delivery will be stopped and another target point will be selected for further applications. Any additional RF applications located within a 6-mm distance from the first application will be considered as part of the same target point–suspected SOO. On the contrary, all RF applications located beyond this 6-mm distance will be considered as additional target points.

### 4.6 PRE-DISCHARGE

The pre-discharge visit must be performed within 3 days of the ablation procedure and before the patient is discharged from hospital. For all patients, the following procedures must be performed:

- Adverse Events Notification (if applicable)
- Protocol Deviation (if applicable)
- Termination (if applicable)

Regarding medications prior discharge, antiarrhythmic drugs will not be reinitiated after the procedure. A control TTE will be advisable in case any procedure-related complication is suspected. Otherwise, it is not required as per protocol.

### 4.7 ONE-MONTH FOLLOW-UP

Clinical follow-up will include an outpatient clinic visit one month after ablation procedure. 12-lead ECG and 24-hour ambulatory Holter monitoring will be performed. Successful ablation will be defined as at least an 80% reduction in the 24-hour burden of PVCs at one month post-procedure, since recurrences may be detected very soon after the catheter ablation.

## 5. STATISTICAL METHODS

### 5.1 SAMPLE SIZE

For sample size calculation, a superiority design was assumed. Null hypothesis is considered at the outset that the two annotation methods (M- and WF-methods) are on average equal in terms of mapping success (as defined in section 2.4), whereas the alternative hypothesis states that the proposed annotation methods are not equal. Based on historical controls, the acute mapping success was considered to be about 60% for the M-method, and 85% for WF-method. The Type I error was set to a value of 5%. The Type II error was set equal to 20%, with a statistical power of 80%. Given these assumptions, a sample size of 98 is estimated (49 patients per group).

### 5.2 STATISTICAL ANALYSIS

Statistical analysis will be performed using SPSS (version 23, SPSS Inc., Chicago, IL). Continuous variables will be expressed as mean  $\pm$  SD or median (range), and will be compared with the Student t test. For categorical variables, data will be expressed as percentages. Proportions will be compared with  $\chi^2$  test. Differences will be considered statistically significant when  $p < 0.05$ .

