Given these limitations of conventional assessment of LAT in both bipolar and unipolar EGMs, increasing efforts have attempted to develop automatic algorithms for activation mapping. Recently, El Haddad et al described an automated algorithm that detects the maximal  $-dV/dt$  in the U-EGM within the window demarcated by the B-EGM that achieved the highest accuracy in algorithmic mapping of atrial and ventricular tachycardia. This algorithm, once integrated into an electroanatomical navigation system, allows the automatic annotation of the LAT during activation mapping. However, data about its utility and accuracy in PVC ablation procedures are scarce. A recent study by our group including 40 patients that underwent PVC ablation showed that the correlation between manual LAT annotation by expert electrophysiologists and automatic annotation by the Wavefront system was good. However, WF-annotation systematically underestimated LAT, especially in LVOT. In terms of accuracy in the SOO identification, the effective RFp was equally well identified with both annotation approaches. However, a randomized study comparing ablation guided by conventional LAT annotation vs. guided by automatic LAT annotation should be performed in order to confirm the efficacy of Wavefront-guided annotation during PVC ablation procedures.

The present randomized study aims to analyze the accuracy of this novel algorithmic method, based on automatic annotation of the maximal negative slope of the U-EGM within the window demarcated by the B-EGM (Wavefront, CARTO, Biosense Webster, Diamond Bar, CA, USA) by comparison with conventional manual annotation in a multicenter cohort of patients referred for PVC ablation. Further on, the automatic annotation of LAT will be aided by the ECG recognition pattern algorithm (included in the last version of CARTO), which is intended to avoid wrong annotation of ventricular complexes other than the clinical PVC. This automatic acquisition process

(LAT and ECG pattern) will be referred to from now on as WF-method. We hypothesize that automatic LAT annotation using WF-method could be superior to conventional, manual annotation in terms of mapping success and could reduce both procedure time and radiofrequency time.

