### 2.3 OBJECTIVES

In order to assess the potential benefits of automatic instead of manual LAT annotation during ablation procedures of premature ventricular complexes (PVCs), the following objectives will be assessed:

1. To compare the ability of both annotation systems (WF vs. M-method) to accurately identify the PVC site of origin (SOO) and propagation pattern. To compare the rates of mapping success (see definition in the next section) between both methods.
2. To assess other procedural outcomes obtained from both annotation systems: Procedure time, mapping time, RF time, number of RF applications.
3. To compare the clinical outcomes (PVC burden at one month after procedure) between both annotation approaches.

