### 2.5.2 SECONDARY ENDPOINTS

The following secondary endpoints will be considered:

1. Mapping time.
2. Number of mapped chambers.
3. Accuracy of proposed algorithm (see Appendix C) for selection of first chamber to map.
4. Number of target points.
5. RF time.
6. Number of RF applications.
7. Acute procedure success, as defined in the previous section.
8. Clinical success (reduction of, at least, 80% in the 24-hour PVC burden one month after the procedure).

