**MAPPING DATA:**

- **First mapped chamber:** RVOT / LVOT / Coronary sinus / Tricuspid annulus / Mitral annulus
- **Sublocation of 1st mapped chamber:** .....
- **Additional mapped chambers (sort chronologically, specify sublocation if needed):**
  1. ....
  2. ....
  3. ....
- **First chamber mapping time:** Start: .....:..... Finish: .....:..... Total: ..... min  
Second chamber mapping time: Start: .....:..... Finish: .....:..... Total: ..... min  
Third chamber mapping time: Start: .....:..... Finish: .....:..... Total: ..... min
- **Total mapping time (all chambers):** Start: .....:..... Finish: .....:..... Total: ..... min

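### Does testing times with a Student t test while allowing a median summary (section 5.2) call for a different analysis?

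*Combined protocol and SAP*

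**What the plan says.** Section 5.2 has one sentence on continuous variables: they are shown as mean ± "SD or median (range), and will be compared with the Student t test". It gives no rule for choosing the summary, no transformation or rank test, and no effect estimate with an interval.

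The outcomes concerned are secondary. Section 2.3 lists, under objective 2, "Procedure time, mapping time, RF time, number of RF applications". Mapping time is first in the list of section 2.5.2, which also contains RF time but not procedure time. The Background expects that the automatic method "could reduce both procedure time and radiofrequency time".

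For PVC burden, the endpoint listed in section 2.5.2 is binary: "Clinical success (reduction of, at least, 80% in the 24-hour PVC burden one month after the procedure"). It falls under the chi-square test.

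**The concern.** A median printed beside a t-test p value puts two quantities side by side. With skewed times they could point in different directions, and a team could choose the summary after seeing the data.

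There is also an argument about power. In the manual arm, "An experienced electrophysiologist will perform the annotation of LAT in each acquired point" (section 4.5.3.1). In the other arm, "The annotation of LAT in each acquired point will be automatically performed" (section 4.5.3.2). A saving at every point suggests a proportional reduction. Section 4.5.3 sets "The minimum density of points required to obtain an acceptable map", which suggests a floor. Appendix B records "Total mapping time (all chambers"), with room for up to three chambers, which suggests a right tail. For such data, a t test on raw minutes could miss a real saving that a log-scale or rank test would find. No time outcome has its own power calculation.

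**Working it through.** **1. The plan's own figure.** Section 5.1 gives 60% v 85% mapping success, 5% type I error, 80% power and 49 per group. With a two-sided test and pooled variance under the null:

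n = [1.96·√(2·0.725·0.275) + 0.842·√(0.60·0.40 + 0.85·0.15)]² / 0.25² = (1.238 + 0.510)² / 0.0625 = 48.9, so 49 per group and 98 in all.

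This figure reproduces. It concerns the binary primary endpoint and does not depend on how times are tested.

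**2. Can mean and median truly disagree?** Take a time as floor f plus a log-normal excess with median m and log-SD σ. Suppose the automatic method multiplies the excess by r. The median difference is (1 − r)·m and the mean difference is (1 − r)·m·exp(σ²/2). Both have the same sign. For example (assumed values), f = 10 min, m = 20 min, σ = 0.7 and r = 0.7 give a median saving of 0.3·20 = 6.0 min and a mean saving of 0.3·20·exp(0.245) = 7.7 min. Under this model, opposite signs in a trial are sampling noise.

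**3. How often does noise produce a conflict?** Simulation with 49 per arm, log-normal times (assumed) and two-sided 0.05:

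| SD of log | Reduction | Power, raw t | Mean v median, opposite signs | Same, among significant t tests | Geometric mean v median, opposite signs |
|---|---|---|---|---|---|
| 0.5 | 15% | 32% | 9% | 0.1% | 8% |
| 0.8 | 20% | 22% | 14% | 0.3% | 10% |
| 1.0 | 20% | 14% | 21% | 1.1% | 13% |

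A significant p value that contradicts the medians occurs in about 0.32·0.1% = 0.03%, 0.22·0.3% = 0.07% and 0.14·1.1% = 0.15% of all trials. The last column shows that a log-scale estimate would also often differ in sign from the medians.

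**4. Power, purely log-normal times.**

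| SD of log | Reduction | Raw t | Log t | Mean v median, opposite signs |
|---|---|---|---|---|
| 0.3 | 15% | 74% | 75% | 1.5% |
| 0.4 | 20% | 75% | 78% | 1.4% |
| 0.5 | 25% | 76% | 81% | 1.0% |
| 0.8 | 40% | 77% | 88% | 0.8% |
| 1.0 | 40% | 52% | 71% | 3.3% |

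With no true difference, the raw t test rejects in 4 to 5% of trials. This model favours the log scale by construction, and even so the gain is small up to an SD of log of 0.5.

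**5. Mapping time as a sum of one to three chambers.** Log t minus raw t, in points of power. The floor, chamber mix and spread are all assumed.

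- The whole time is cut by 25%, with a floor per chamber: +6 to +16 if 75% of patients need one chamber, +1 to +9 if 60% do, −3 to +4 if 50% do.
- The same cut with no floor: −11 to +8.
- Only the time above the floor is cut: at most about +7, and down to about −12 even with a floor.

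The last case is plausible. Section 4.5.3 requires a 2-second stability period before each point in both arms, and annotation does not shorten it or the catheter movement. The ratio between arms is constant only if annotation takes the same share of the time in every patient.

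**6. The other outcomes.** RF time was modelled from section 4.5.4 and the 60% and 85% rates. Raw t v log t gives 91% v 85% if patients are alike and 77% v 88% if they differ strongly, so no scale is clearly better. No calculation supports a log scale for procedure time. For burden, assuming one-month success of 70% v 90%, the listed responder comparison has 72% power, against 51% for a t test on one-month values and 55% with adjustment for baseline. The plan already uses the strongest of the three.

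**7. The missing interval.** The t test has its own: mean difference ± 1.985·s·√(2/49) = mean difference ± 0.40·s, where s is the pooled SD and there are 96 degrees of freedom. It needs no choice beyond the test already named.

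**The case for a change.** The best case for a change is strong skew. With one chamber, an assumed control median of 30 min, a floor of 10 min, a log-SD of 1.0 and the excess cut by 30%, power is 29% for raw t and about 40% for log t or a rank test. With a floor of 15 min and the whole time cut by 20%, it is 31% for raw t, 56% for log t and 66% for a rank test. The means and medians would also be noisy companions in such data, and a pre-specified estimate would cost only two sentences.

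The arithmetic stands, and so does the remark that section 5.2 is loose. What does not stand is the step to a different analysis. A log-SD of 1.0 for mapping time is an assumption with no support in the documents. At 0.3 the tests are practically equal, and for normal data the order reverses slightly (80% for t, 78% for the rank test). Once several chambers are summed, or the saving falls only on the time above the floor, the log scale can lose. It also replaces mean minutes saved, a natural target for a time recorded in minutes, with a ratio. Naming the estimate would be tidy, but it would alter no test and no result.

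**Conclusion.** No change follows. The pairing of a median summary with a t test is real, but the test validly compares means at 49 per arm. A significant result that contradicts the medians occurs in about 1% of significant trials or fewer. This rests on log-normal times with the same log-SD in both arms, log-SDs of 0.5 to 1.0, and reductions of 15 to 20%. At the larger effects used for the power comparison, opposite signs occur in about 1 to 3% of all trials.

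The log scale is a trade-off whose direction the documents do not settle. With a floor and one to three chambers, it ranges from about 16 points gained to about 12 lost. What remains is a gap that an analyst fills sensibly: report the mean difference and its 95% interval with the t test, and show medians as description. RF time and the responder endpoint keep their present tests in any case. The primary comparison and the sample size of 98 are unaffected.

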## APPENDIX B: Data collection sheet

**PATIENT ID:** .....

**ABLATION DATE:** ..... / ..... / .....

**CENTER:** Clínic / German Trias i Pujol / Virgen del Rocío / Puerta del Mar / Guglielmo da Saliceto

### DEMOGRAPHICS:

- **DOB:** ..... / ..... / .....
- **Age:** .....
- **Sex:** M / F
- **Height:** ..... cm
- **Weight:** ..... Kg
- **Hypertension:** NO / YES
- **Diabetes:** NO / YES
- **Dyslipidemia:** NO / YES
- **Smoker:** NO / YES
- **COPD:** NO / YES
- **Sleep apnea:** NO / YES
- **CLINICAL SCORE** (1 point for: HTA, male, > 50 y.o.) = .....

### HEART DISEASE:

- **Cardiomyopathy:** Ischemic / Valvular / Idiopathic / Hypertensive / Other:  
.....
- **Ischemic cardiomyopathy:** Anterior / Inferior / Lateral / Septal / RV myocardial infarction
- **NYHA Functional Class:** I / II / III / IV
- **ICD:** NO / YES: Primary / Secondary prevention
- **Atrial fibrillation:** NO / YES: Paroxysmal / Persistent / Long-lasting / Permanent
- **Conduction disease:** NO / YES: .....
- **Basal QRS duration (ms):** .....

### PVC MORPHOLOGY:

- **Monotopic:** YES / NO
- **PVC-QRS duration:** ..... ms
- **PVC coupling interval:** ..... ms
- **Fixed coupling interval?**: NO / YES
- **Axis:** Superior / Inferior || Left / Right
- **Transition:** V1 / V2 / V3 / V4 / V5 / V6
- **24-h Holter % of PVCs:** .....
- **24-h Holter number of PVCs:** .....
- **Other morphologies/Notes:** .....

**MEDICATIONS:**

- **Betablockers:** (.....) Dose (.....) - **Amiodarone:** NO / YES: Dose (.....)
- **Flecainide:** NO / YES: Dose (.....) - **Digoxin:** NO / YES: Dose (.....)
- **ACEI:** (.....) Dose (.....) - **ARA-II:** (.....) Dose (.....)
- **Spironolactone:** NO / YES: Dose (.....) - **Furosemide:** NO / YES: Dose (.....)
- **Others:** .....

**IMAGING AND BLOOD TESTS:****ECHOCARDIOGRAPHY:**

- **LVEF** (Simpson 4C): ..... %
- **LVEDD:** ..... mm - **LVESD:** ..... mm
- **LVEDV:** ..... mL - **LVESV:** ..... mL
- **Segmental wall motion abnormalities:** NO / YES: Segments: .....
- **Significant valvular disease:** NO / YES: Specify: .....

**MRI:**

- **MRI MODALITY:** 1.5 Tesla / 3 Tesla
- **LVEF** (Simpson 4C): ..... %
- **LVEDD:** ..... mm - **LVESD:** ..... mm
- **LVEDV:** ..... mL - **LVESV:** ..... mL
- **Location of LGE:** Subendocardial / Intramyocardial / Subepicardial / Transmural
- **Distribution of LGE:** Linear / Patchy / Others: .....

**CARDIAC CT:** NO / YES**BLOOD TESTS:**

- **BNP:** ..... pg/mL - **NT-proBNP:** ..... pg/mL

**ABLATION PROCEDURE:**

- **Annotation system:** MANUAL / WAVEFRONT
- **Ablation catheter:** Navistar ThermoCool / ThermoCool SmartTouch
- **Deflectable sheath (Agilis):** NO / YES
- **First vascular access:** Femoral artery / femoral vein

**MAPPING DATA:**

- **First mapped chamber:** RVOT / LVOT / Coronary sinus / Tricuspid annulus / Mitral annulus
- **Sublocation of 1st mapped chamber:** .....
- **Additional mapped chambers (sort chronologically, specify sublocation if needed):**
  1. ....
  2. ....
  3. ....
- **First chamber mapping time:** Start: .....:..... Finish: .....:..... Total: ..... min  
Second chamber mapping time: Start: .....:..... Finish: .....:..... Total: ..... min  
Third chamber mapping time: Start: .....:..... Finish: .....:..... Total: ..... min
- **Total mapping time (all chambers):** Start: .....:..... Finish: .....:..... Total: ..... min

